Endpoints:	Week 0: Baseline assessment, pre-intervention	
	Week 2, 4, 8, 16: Intermediary follow-up assessments Week 26: Final follow-up assessment	
Sample Size:	40 individuals.	

Summary Of Eligibility Criteria:	Aged between 18-65 at study entry. Meet DSM-5 criteria for a current depressive episode and exceed thresholds indicating presence of mixed features. Undergoing antidepressant treatment (stable intervention/dose unchanged for >6 weeks). No diagnosis of bipolar disorder received. No other severely impairing health condition. No contraindications to lithium treatment (including currently taking lithium). No significant suicidality.		
Intervention (Description, frequency, details of delivery):	Open label lithium orotate supplement as available commercially, 20mg once per day. Participants will be instructed to begin taking the supplement the day after the baseline assessment for a period of up to six months. If participants prefer to move to a lower dose, they can titrate down to 15mg, 10mg or 5mg. Intervention is self-managed, but participants are provided with information about the supplement and have access to the research team to answer any questions or provide further information. Participants who discontinue will remain in the study, although will not be required to attend intermediary follow- up visits, which collect information related to the intervention. We will ask them to attend the final endpoint visit, however.		
Comparator Intervention:	n/a		
Maximum Duration Of Treatment Of A Participant:	6 months / 26 weeks (i.e., from baseline up until the final follow-up assessment). Participants are permitted to discontinue the supplement at any time they wish.		
Version And Date Of Final Protocol:	[to be completed]		
Version And Date Of Protocol Amendments:	n/a as yet		

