# 6. Study Objectives and Design

## 6.1. Study Objectives

This research aims to elucidate LiOr's plausibility, at a known safe dose, over an extended period in a preliminary study. This is a feasibility study comprising the preliminary work required prior to formal trials examining commercially available LiOr supplementation for DMF. No specific hypotheses are therefore proposed. In this open label study, people who constitute a target population for LiOR will be invited to take commercially available LiOr for up to six months to establish its plausibility as a putative intervention for trials. The specific objectives are to investigate up to six months of open-label 20mg daily LiOr to identify its within-subjects effects on the following as co-primary outcomes:

1. The potential to examine bioavailability of LiOr (i.e. whether lithium is present at detectable levels in the serum using a standard laboratory lithium test), assessing lithium levels in serum.

2. The acceptability of 20mg daily LiOr over 6 months (assessed by self-report adherence and discontinuation rates) to inform a future study design.

3. Description of any positive and/or negative experiences of 20mg daily LiOr over 6 months (assessed via participant-report) to inform a future study design.

4. The feasibility of the protocol including intervention delivery and assessment visits (including assessments mentioned above, plus putative primary (mood) and secondary (functioning, cognition) outcome measures and assessment of potential confounders). Overall feasibility will be assessed via missing data and study withdrawal rates.

An exploratory analysis of change will be undertaken as secondary objectives for measures over time to inform a future definitive study design:

1. LiOR's biological effects, through assessment of key candidate blood-based biomarkers, namely neuroprotective growth factors (BDNF, VEGF) and inflammatory cytokines (IL-6, TNFa, IL-1b, IL-8, CRP) between week 0 and week 26.

2. LiOr's effects on mood, through assessing changes in mood ratings between week 0 and week 26.

3. LiOr's effects on cognition and functioning, through assessing changes in cognitive and psychosocial function between week 0 and week 26.

These aims will be met via within-subjects comparisons for each timepoint relative to baseline (weeks 2, 4, 8, 16, 26).

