## 9.6. Withdrawal of Participants

We will highlight to all participants that they are free to withdraw from the study at any time, without prejudice or consequences for either their clinical care, or involvement in any other research studies. Similarly, therapy can be discontinued at any point, if a participant withdraws from the study or if a participant decides they no longer wish to continue the intervention. Researchers will also be available throughout the study course to answer further questions about withdrawal. The investigator also has the right to withdraw patients from the therapy and/or study, for any reason e.g., if a participant loses the capacity to consent to the study, they will be withdrawn. This will be assessed by researchers during every contact with participants (e.g., phone calls, study appointments).

Should a participant decide to withdraw from the study, all efforts will be made to report the reason for withdrawal as thoroughly as possible. Importantly, LiOr discontinuation does not constitute as a withdrawal from the study. Thus, should a patient withdraw from the intervention only, efforts will be made to continue to obtain follow-up data, with the permission of the patient; participants who wish to withdraw from LiOR will be asked to confirm whether they are still willing to provide the study data already provided for research.

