## 9.7. Expected Duration of Study

The total study duration for a given participant will be 26 weeks. Week 0 will comprise the baseline assessment and LiOR initiation will occur as soon as feasible after this. Intermediary assessments will be conducted at week 2, week 4, week 8 and week 16, followed by the final follow-up assessment and discontinuation of LiOR at week 26. The beginning of the study overall will be Week 0 (baseline assessment) of the 1st participant, estimated October 2024, and the end of the study will be one month after the last week of the 40th participant's follow-up assessment, estimated to be in August 2025, to allow for sample analysis.

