## 12.1. Sample Size

As an initial feasibility study, a sample size calculation is not warranted. However, a sample of 40 participants permits estimation of a 50% dropout rate to within a 95% confidence interval of +/-15%.[Research Design Service. NIHR. Available at: https://www.rds-london.nihr.ac.uk/resources/justify-sample-size-for-a-feasibility-study/]. The existence of six repeated measures and focus on within-subjects change/variability will help boost power to observe effects without aiming to determine statistical significance of effects with any precision.

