## 12.2. Analysis

Intention-to-treat analyses will be undertaken. In a few cases, a sensitivity analysis will be carried out, excluding non-adherent participants (these are specified below, where this applies).

Final analyses will be conducted after data collection has been completed and data cleaned. However, it is worth noting that an interim analysis is planned in May 2025 for all primary analyses below. This is for the purpose of initial pilot data to be included in funding applications being submitted for a feasibility study. No changes to the protocol or any procedures will be made based on this.

Variables will be summarised using descriptive statistics (i.e., mean and standard deviation [SD] or median and interquartile range [IQR] or frequencies and proportions, as appropriate).

Analyses pertaining to each outcome are listed below:

1. LiOR bioavailability as assessed by lithium levels in serum. This will be analysed descriptively, as above. Intraand inter- participant variation will be calculated. Overall changes over time may be assessed using a repeatedmeasures ANOVA (including only adherent participants taking a stable dose) to inform a potential future trial design.

2. LiOR acceptability as assessed by adherence rates (TRQ) and discontinuation. Rates of adherence (< 20% missed) will be assessed descriptively for each timepoint, and extent of adherence will also be described as a continuous (total TRQ score) measure. Rates of discontinuation (participant-report) will be described. Continuous adherence scores (for participants not discontinuing LiOR) over time will be tentatively compared using a repeated-measures ANOVA to inform a potential future trial design.

3. Subjective experiences of LiOR: negative experiences will be described via continuous LiSERS score measure, and positive experiences will be reported as participant-reported rates (yes/no to those listed). LiSERS scores over time (adherent participants only) will be compared using a repeated-measures ANOVA (possibly including dose as a between-subjects factor, pending dose variation within and between participants) to inform a potential future trial design.

4. Protocol feasibility as assessed by the rates (assessed descriptively) of attrition from the study, and of visits missed, and specific data for the putative primary outcomes i.e., mood measures.

There are three secondary outcomes, analysed as exploratory indications of change to inform a future definitive study design:

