1. LiOR's biological effects, through assessment of key candidate blood-based biomarkers, namely neuroprotective growth factors (BDNF, VEGF) and inflammatory cytokines (IL-6, TNFa, IL-1b, IL-8, CRP) throughout the study. This will be examined using a repeated-measures ANOVA according to the intention-to-treat principle, with a sensitivity analysis to examine only adherent participants.

2. LiOr's effects on mood, through assessing changes in mood ratings (M3VAS, ISS, IDS, YMRS) throughout the study. These will be examined using a repeated-measures ANOVA according to the intention-to-treat principle, with a sensitivity analysis to examine only adherent participants.

3. LiOr's effects on cognition and psychosocial function, through assessing changes in THINC-IT and FAST scores respectively, throughout the study. These will be examined using a repeated-measures ANOVA according to the intention-to-treat principle, with a sensitivity analysis to examine only adherent participants.

Ancillary exploratory analyses will examine other wellbeing outcomes (e.g., EQ5D), service use, and a potential impact of bipolar features on outcomes during the study. Additional exploratory analyses using the data collected may be conducted.

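### As written, the repeated-measures ANOVA for the secondary outcomes is not intention-to-treat: it loses most participants who stop LiOr before week 16, even if they attend week 26

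*Protocol*

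**What the plan says.** Section 12.2 opens with a general rule: "Intention-to-treat analyses will be undertaken". For mood, and again for cognition and psychosocial function, it then says: "These will be examined using a repeated-measures ANOVA according to the intention-to-treat principle, with a sensitivity analysis to examine only adherent participants". The biomarker item is worded to the same effect. All three are to be assessed over the whole study.

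The schedule has six assessments. Section 9.7: "Intermediary assessments will be conducted at week 2, week 4, week 8 and week 16, followed by the final follow-up assessment", with baseline at week 0. Section 12.1 relies on this: "The existence of six repeated measures and focus on within-subjects change/variability will help boost power".

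On stopping the supplement, the synopsis says: "Participants who discontinue will remain in the study, although will not be required to attend intermediary" follow-up visits, on the ground that these visits collect information about the intervention. Those participants are asked to come to week 26. Section 9.6 adds that after withdrawal from the intervention only, "efforts will be made to continue to obtain follow-up data, with the permission of the patient", without naming visits.

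Section 6.1 frames the secondary objectives as change between week 0 and week 26, and then adds: "These aims will be met via within-subjects comparisons for each timepoint relative to baseline (weeks 2, 4, 8, 16, 26").

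**The concern.** The visits from which stoppers are released are not only about the intervention. Table 1 and Section 10.1 place the mood scales, the cognitive battery and the blood test at weeks 2, 4, 8 and 16, and these are the outcomes that Section 12.2 analyses. So the attendance rule produces missing outcome values that depend on stopping LiOr, and the named method then removes anyone with a missing value. A participant who stops at week 5, skips weeks 8 and 16 and returns at week 26 gives the week 0 and week 26 values that Section 6.1 asks for, yet contributes nothing to the ANOVA.

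Two things are at stake. The estimated change, and the SDs and correlations that go with it, would come mainly from people who stayed on LiOr, although they are meant to inform a later trial. And the set labelled intention-to-treat moves towards the adherent-only set, so agreement between the two would reassure more than it should.

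**Working it through.** **The plan's own figure.** Section 12.1 says that "a sample of 40 participants permits estimation of a 50% dropout rate" to within 15 points either side (95% CI). The Wald half-width is 1.96 × √(0.5 × 0.5 / 40) = 15.5 points, and the Wilson half-width is 14.8 points. The stated figure is sound as a rounded value. It is a precision statement about dropout and is not used below as a forecast.

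**Inputs from the protocol.** N = 40; six assessments (weeks 0, 2, 4, 8, 16, 26); stoppers not required at weeks 2 to 16 but asked to attend week 26.

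**Assumptions, not in the protocol.** A share d stops LiOr (10%, 30%, 50%). Stoppers skip every visit from which they are released and attend week 26. Stopping times are either all before week 16 or uniform over 26 weeks. Any other post-baseline visit is missed with probability m (0, 5%, 10%), independently.

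**Expected complete profiles.** C = 40 × [(1 − d) + d × L] × (1 − m)^5, where L is the share of stoppers who stop after week 16. L = 0 if all stop before week 16, and L = 10/26 = 0.385 if stopping is uniform.

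Example, d = 30%, uniform, m = 0: 40 × (0.70 + 0.30 × 0.385) = 32.6.

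| d | All stop before W16, m = 0 | Uniform, m = 0 | Uniform, m = 5% | Uniform, m = 10% | Share of complete set who never stop (uniform) |
|---|---|---|---|---|---|
| 10% | 36 | 37.5 | 29.0 | 22.2 | 36/37.5 = 96% |
| 30% | 28 | 32.6 | 25.2 | 19.3 | 28/32.6 = 86% |
| 50% | 20 | 27.7 | 21.4 | 16.4 | 20/27.7 = 72% |

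The last column reaches 100% only if all stopping comes before week 16.

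**Illustrative effect on the estimate.** Suppose those who never stop change by −8 points, stoppers by 0, and d = 30%.
- All 40 participants: −8 × 0.70 = −5.6.
- Complete profiles, uniform stopping: −8 × 28/32.6 = −6.9.
- Complete profiles, all stopping before week 16: −8.0.

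The values −8 and 0 are chosen only to show direction. If stoppers improved more, the bias would reverse.

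**One simulated dataset as a check on the mechanism.** With 12 of 40 stopping at uniform times, the same −8 and 0, and everyone seen at week 26, 31 of 40 had all six visits. A balanced ANOVA routine refused the full data as unbalanced. The week 0 to week 26 change was −8.2 in complete profiles and −6.3 from a random-intercept mixed model on all 40; the built-in mean is −5.6. A single dataset carries sampling noise, so only the retained numbers and the direction should be read from it.

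**Exception.** Table 1 marks FAST at weeks 0 and 26 only, while the list of wellbeing measures in Section 10.1 gives it at every timepoint. On the Table 1 schedule, the FAST analysis has two timepoints and keeps every stopper who attends week 26.

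**The case against.** The best defence is that these outcomes are exploratory, in a single-arm feasibility study with no hypotheses, and that handling of missing data is often left to a SAP, which is not at hand. The first part stands and limits the severity. The second stands only in part: the protocol itself fixes both the method with its label and the attendance rule, and no SAP can recover visits that were never requested.

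Several stronger readings are tempting, and the documents do not support them.
- *Repeated-measures ANOVA can never be intention-to-treat here.* After imputation it could include everyone, and a plain week 0 to week 26 comparison would keep stoppers who return. The protocol simply states neither as its handling of incomplete profiles.
- *Only those who persist with LiOr are analysed.* Stoppers are not required at the middle visits, but they are not barred. Those who stop after week 16 were due at every earlier visit and are asked back at week 26.
- *The adherent-only analysis cannot show a difference.* Adherence is an 80% threshold on the TRQ (Section 7.3). Participants below it who have not stopped stay in the main set and leave the sensitivity set.
- *The protocol plans for 50% dropout, so at most 20 of 40 would be analysed.* Section 12.1 only illustrates precision, and Section 9.6 separates stopping LiOr from leaving the study. Twenty is the result at 50% stopping only if all of it comes before week 16.
- *The synopsis and Section 9.6 contradict each other.* They are compatible, but they leave open what is sought from stoppers at weeks 2 to 16.
- *The ANOVA cannot deliver the comparisons in Section 6.1.* Contrasts within an ANOVA are routine. The gap is that Section 12.2 names none.

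**Conclusion.** The point holds as a conflict inside the protocol. Followed literally, Section 12.2 applies a complete-profile method under an intention-to-treat label while the synopsis makes incomplete profiles the expected result of stopping LiOr early. Most participants who stop before week 16 would be lost to the six-visit analyses; late stoppers and non-adherent continuers would remain.

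The size depends on the rate and timing of stopping, which the protocol does not give, and any other missed visits reduce the complete set further. Overstatement of change follows only if stoppers improve less, which is plausible but assumed.

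The co-primary outcomes are not affected: they are mainly descriptive, and their ANOVAs are openly restricted to adherent or continuing participants. This is a point that should be fixed rather than one that must be.

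**What to change.** 1. In Section 12.2, for the secondary outcomes, replace repeated-measures ANOVA with a linear mixed model that uses every participant with any data, with visit as a categorical factor. An unstructured covariance over six visits has 6 × 7 / 2 = 21 parameters, so name a structure that 40 people can support and a simpler fallback in advance.
2. Report week 26 minus week 0 with its 95% CI as the main contrast, in line with Section 6.1, and the other visits as supportive. Keep the adherent-only analysis as the sensitivity analysis.
3. Align the synopsis with Section 9.6: state that participants who stop LiOr are still invited, voluntarily, to the outcome assessments at weeks 2 to 16. The mixed model relies on missingness being explained by observed data, so these values matter even with the better model. This wording is the more urgent part, because uncollected data cannot be recovered.
4. Reconcile the FAST schedule between Table 1 and Section 10.1.

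The cost is wording, slightly more analysis work and a small voluntary burden on participants who stop. That burden is real, since remote self-report cannot replace blood samples.

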#### 6.2. Study Design

A single site, one arm unblinded open label study investigating the effects of LiOr supplementation (20mg, once per day) for up to six months. We will recruit 40 people for this feasibility study.

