#### 6.3. Study Flowchart

Table 1: Summary of study procedures and measures.

Procedures/Measures	Screening	Baseline (W0)	Intermediary (W2, 4, 8, 16)	Follow-up (W26)
Eligibility assessment [questions, MINI suicide, bipolar, & MDD  ,	Х			
Informed consent		Х		
LiOr provision		Х	Х	
Patient information	Х			
Sociodemographic		Х		х
Illness history [questions, HCL  , TEMPS 16* ]		Х		
Service use and health-related quality of life (EQ5D) 		Х		Х
Cognitive battery (THINC-IT  )		Х	Х	Х

Procedures/Measures	Screening	Baseline (W0)	Intermediary (W2, 4, 8, 16)	Follow-up (W26)
Mood self- (ASRM  / M3VAS  / GAD7  / ISS  ) & investigator- report (IDS  / YMRS 		Х	Х	х
Functioning [FAST  ]		Х		Х
Blood test	Х	Х	Х	Х
Subjective experiences (LiSERS  )			Х	Х
Adherence (TRQ  )			Х	Х

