#### Sociodemographic/illness-history/service use questions

- Date of birth, gender, ethnicity, height, weight, education level (highest level of education), employment status, substance use (e.g., smoking, alcohol), stressful life events within the past 12 months [baseline only]
- Current health symptoms [week 0 and 26]
- Current pharmacological or other medical treatments (type, dose, frequency of use, duration of use) [all timepoints]
- Previous use of lithium [baseline only]
- Use of healthcare and related services [week 0 and 26]
- Psychiatric comorbidities (questions) [week 0 and 26]
- Bipolar risk measures (questions; MINI bipolar section, HCL, TEMPS) [week 0 and 26]

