#### Wellbeing measures

- Low mood: The Maudsley 3-item visual analogue scale (M3VAS) and investigator-rated Inventory of Depressive Symptoms (IDS) [all timepoints]
- Anxiety: The Generalised Anxiety Disorder 7-item scale (GAD7) [all timepoints]
- Elevated mood: The internal states scale (ISS) and investigator rated Young Mania Rating Scale (YMRS) [all timepoints]
- Functional/wellbeing measures [EQ5D[week 0 and 26], FAST[all timepoints]]

Participants will, at the end of the assessment, be provided with one pot containing 60 LiOR capsules (for weeks 0 to 2). They will also be provided with an information sheet regarding LiOr, and instructed to begin taking the supplement the next day and once each day thereafter.

The researcher will offer two aids to help participants remember to take the supplement: participants can choose to receive a daily text message from the team to remind them to take their daily LiOR, or they can (along with the researcher if desired) set themselves an alarm/reminder for themselves.

The researcher will subsequently send a letter of notification regarding the study (and information about LiOR) to the participants' named Healthcare Professional.

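### Table 1 and the visit text disagree on when FAST, HCL, probably TEMPS, and ASRM are collected, so the planned six-timepoint FAST analysis may lack its week 2 to 16 data

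*Protocol*

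**What the plan says.** **FAST.** The Table 1 row "Functioning [FAST" (section 6.3) is marked under baseline and week 26, with nothing under the intermediary visits. The wellbeing list in section 10.1 has "FAST 23 [all timepoints", and the entries for weeks 2, 4, 8 and 16 repeat the wellbeing measures. Section 12.2, secondary outcome 3, plans a repeated-measures ANOVA "assessing changes in THINC-IT and FAST scores respectively, throughout the study". Section 6.1 words the functioning objective as change from week 0 to week 26, then closes by saying that the aims are met by comparing each of weeks 2, 4, 8, 16 and 26 with baseline.

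**HCL and TEMPS.** Table 1 places both in the illness-history row, marked at baseline only. Section 10.1 places both in the line that begins "Bipolar risk measures (questions; MINI bipolar section" and tags that line for weeks 0 and 26.

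**ASRM.** The Table 1 row that begins "Mood self- (ASRM" is marked at baseline, at the intermediary visits and at week 26. Section 10.1 names only ISS and YMRS for elevated mood. Section 12.2 plans "assessing changes in mood ratings (M3VAS, ISS, IDS, YMRS) throughout the study", without ASRM.

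**Co-primary objective 4.** Section 6.1 covers mood, functioning, cognition and confounder assessments and says "Overall feasibility will be assessed via missing data and study withdrawal rates". Section 12.2, item 4, is narrower: attrition, visits missed, and data for the mood measures.

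**The concern.** Section 10.1 opens by pointing to Table 1 as the description of what happens at each visit, and then describes the visits again in text. Neither is given precedence, so a team may follow either. A team that works from the table will not give FAST at four of the six visits, and no later analysis document can recover forms that were never given.

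Two things are at stake. The first is the secondary functioning analysis, which sections 6.1 and 12.2 both describe as running over the intermediate visits. The second is the count of forms due for any instrument-level missing-data rate. That count matters more than usual here because missing data are part of a co-primary feasibility objective.

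**Working it through.** **Inputs.** Section 6.2: "We will recruit 40 people for this feasibility study". Visits at weeks 0, 2, 4, 8, 16 and 26, that is six measurement points, the number that section 12.1 also uses.

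**The protocol's own figure.** It gives no count of forms due. Its one precision figure, ±15% for a 50% dropout rate (section 12.1), reproduces as 1.96 × √(0.5 × 0.5 / 40) = 0.155, or 15.5 points. It rests on 40 participants and not on the instrument schedule, so this point leaves it untouched.

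**Forms due = 40 × number of scheduled timepoints.**

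| Instrument | Table 1 | Section 10.1 | Section 12.2 |
|---|---|---|---|
| FAST | 40 × 2 = 80 | 40 × 6 = 240 | analysed over the whole study |
| HCL | 40 × 1 = 40 | 40 × 2 = 80 | not named |
| TEMPS | 40 × 1 = 40 | 40 × 2 = 80 | not named |
| ASRM | 40 × 6 = 240 | not listed | not in the mood list |

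For FAST the difference is 240 − 80 = 160 forms, all at weeks 2 to 16.

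**Effect on the FAST analysis.** With six timepoints and 40 complete participants, the ANOVA time effect has 6 − 1 = 5 and 5 × 39 = 195 degrees of freedom. With weeks 0 and 26 only, it has 1 and 39, and it equals a paired t-test. A check on simulated data with n = 40 gave F(1, 39) = 0.3128 and t² = 0.3128. The week 0 to 26 change can therefore be estimated under either schedule. What is lost under Table 1 is the set of contrasts at weeks 2, 4, 8 and 16. THINC-IT, the other half of this outcome, is at all visits in both places and is unaffected.

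**Effect on co-primary objective 4.**
- Attrition: denominator 40 under either schedule.
- Scheduled visits: 40 × 6 = 240, or 40 × 5 = 200 after baseline, under either schedule.
- Mood-measure data as 12.2 words it: M3VAS, ISS, IDS and YMRS are at all six visits in both Table 1 and 10.1, so 240 forms each and 4 × 240 = 960 together. Of the four disputed instruments, only ASRM can enter. It adds 240 forms if Table 1 decides what counts as a mood measure, and none if 10.1 or 12.2 does.
- FAST, HCL and TEMPS enter only under the broader wording of 6.1.

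**The case against.** The strongest reply is that these are wording slips with limited consequences. The functioning objective in 6.1 is change from week 0 to week 26, and both schedules collect FAST at both ends. The analysis is secondary and exploratory. For FAST, sections 10.1 and 12.2 and the closing sentence of 6.1 all fit six timepoints, so the odd one out is a single table row. Absence of ASRM from the 12.2 list is not an error in itself: GAD7 is collected and not listed there either, and 12.2 allows further exploratory analyses. Most of this stands and sets the size of the point. It does not remove the risk that the table, which is what visit staff are likely to use, leads to FAST not being given at weeks 2 to 16.

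A reader might infer more than the document supports:

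- *The functioning analysis would be impossible.* It would not; it reduces to two timepoints.
- *The co-primary missing-data rate has no denominator.* Section 12.2 ties that rate to the mood measures, and the four scales it analyses have the same schedule in both places.
- *FAST would look 67% missing.* The figure, (240 − 80) / 240 = 66.7%, arises only if every visit is run from Table 1 and then scored against 10.1.
- *Feasibility could be judged good or poor by choice of schedule.* The protocol sets no feasibility threshold, and the rates are descriptive.
- *The visits that participants who stop the supplement need not attend undermine the missed-visit rate.* How to tabulate those visits is detail that can be settled in the analysis plan, and is not part of this conflict.

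The TEMPS conflict is less certain than the rest. Its Table 1 entry carries an asterisk whose footnote is not in the text at hand and may explain the timing.

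**Conclusion.** The point holds as a conflict between schedules that should be corrected. It is clear for FAST, HCL and ASRM, and probable for TEMPS. Its main effect is on FAST: 80 or 240 forms due, and, if Table 1 is followed, a six-timepoint analysis that becomes a comparison of week 0 with week 26. The week 0 to 26 objective survives. For co-primary objective 4, ASRM is the only one of the four instruments that bears on the missing-data rate as 12.2 words it; the others matter only under the wider wording of 6.1. Attrition out of 40 does not change. The counts assume that all 40 participants are recruited and due at all six visits.

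**What to change.** Adopt one schedule across Table 1 and sections 6.1, 10.1 and 12.2.

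1. **FAST.** Either mark it at weeks 2, 4, 8 and 16 in Table 1, which then agrees with 10.1 and 12.2, or keep weeks 0 and 26, correct 10.1, and state the FAST analysis in 12.2 as mean change from week 0 to week 26 with a 95% confidence interval. In the second case, exempt FAST from the closing sentence of 6.1 on comparisons at each timepoint.
2. **HCL and TEMPS.** Give both the same timing in Table 1 and 10.1, and make sure that the note behind the TEMPS asterisk is present.
3. **ASRM.** List it among the 10.1 measures or remove it from Table 1. If it stays, say whether it counts as a mood measure for co-primary objective 4.
4. **Co-primary objective 4.** Have 6.1 and 12.2 name the same instruments for the missing-data rate, defined per instrument as forms completed divided by forms due under the agreed schedule.

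The cost is protocol wording and alignment of the case report forms. Keeping FAST at weeks 0 and 26 needs no data beyond Table 1. Giving it at every visit adds 40 × 4 = 160 forms to what Table 1 requires, all of which 10.1 already asks for.
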